13.6. Interim Analyses

An interim analysis will be performed once 50% of the planned patients have enrolled and those patients have either completed or discontinued the study. The purpose of the interim will be to potentially increase the sample size to maintain statistical power conditioned on the results of the first 50% of patients; or continue as planned if conditional probability of success at Week 14 is above a pre-specified threshold; or to stop the study early for success or for futility if the conditional power is sufficiently low. The study team will only be informed of the recommendation to maintain the original sample size, increase the sample size (by a fixed, pre-specified amount) or discontinue the study for success or for failure (at which point unblinding would occur).

For the primary and key secondary outcomes, the results from before and after the interim will be combined with Cui, Hung, Wang (CHW) methodology (Cui et al, 1999). Full details of the interim analysis will be included in the SAP and finalized prior to execution of the interim analysis.

14. DEFINITIONS, RECORDING, AND REPORTING OF ADVERSE EVENTS

14.1. Definition of Adverse Events

According to International Conference on Harmonization (ICH) guidance E2A, Clinical Safety Data Management: Definitions and Standards for Expedited Reporting, an AE is any untoward medical occurrence in a patient or clinical investigation subject administered a pharmaceutical product and which is not necessarily required to have a causal relationship with this treatment. An AE can therefore be any unfavorable and unintended sign (including an abnormal laboratory finding, for example), symptom, or disease temporally associated with the use of a medicinal product, whether or not considered related to the medicinal product.

A TEAE is an AE that either commenced following initiation of study treatment or was present prior to study treatment but increased in frequency or severity following initiation of study treatment.

14.2. Adverse Event Recording

14.2.1. Coding the Adverse Event

Standard medical terminology should be used in describing AEs. MedDRA® will be used as the standard coding dictionary for AEs and in describing the patient's medical history, and the World Health Organization (WHO) Drug Dictionary will be used to code concomitant medications. Informal descriptions should be avoided.

14.2.2. Severity of Adverse Event

AEs should be graded as mild, moderate, or severe using the following definitions.

- **Mild:** Awareness of signs or symptoms, but easily tolerated and of minor irritant type causing no loss of time from normal activities. Symptoms do not require therapy or a medical evaluation; signs and symptoms are transient.
- **Moderate:** Events introduce a low level of inconvenience or concern to the participant and may interfere with daily activities, but are usually improved by simple therapeutic measures; moderate experiences may cause some interference with functioning.
- **Severe:** Events interrupt the participant's normal daily activities and generally require systemic drug therapy or other treatment; they are usually incapacitating.

To make sure there is no confusion or misunderstanding of the difference between the terms "serious" and "severe," which are not synonymous, the following note of clarification is provided. The term "severe" is often used to describe the intensity (severity) of a specific event (as in mild, moderate, or severe myocardial infarction); the event itself, however, maybe of relatively minor medical significance (such as severe headache). This is not the same as "serious," which is based on patient/event outcome or action criteria usually associated with events that pose a threat to a patient's life or functioning. Seriousness (not severity) serves as a guide for defining regulatory reporting obligations.

14.2.3. Relationship of Adverse Events to Study Drug

The Investigator will assess the potential relationship of the AE to study drug using the following descriptions.

- **Not Related:** This category applies to an AE that is clearly not related to the study drug beyond a reasonable doubt. That is, another cause of the event is most plausible; and/or a clinically plausible temporal sequence is inconsistent with the onset of the event and the administration of study drug and/or a causal relationship is considered biologically implausible.
- **Unlikely Related:** This category applies to an AE that could reasonably be considered caused by something else, and where there is no known or expected response pattern to the suspected study drug.
- **Possibly Related:** This category applies to an AE that follows a reasonable temporal sequence from administration of the study drug and that follows a known or expected response pattern to the suspected study drug, but that could readily have been produced by a number of other factors.

14.3. Serious Adverse Events (SAEs) and Serious Adverse Drug Reactions

Any SAE that occurs at any time during the study, including a clinically significantly abnormal laboratory test result that is considered serious, must be reported to Tonix or its designee(s) so that Tonix may comply with regulatory obligations. If the SAE is life-threatening or fatal, it must be reported to Tonix or its designee(s) immediately, by facsimile and telephone. For these and all other SAEs, an SAE report form must be completed and sent by facsimile or email to Tonix or its designee(s) within 1 working day of the site's initial awareness of the event. These requirements apply equally to all patients, regardless of the study phase or the at-risk patient's treatment assignment or dosage.

A serious adverse event (experience) or reaction is any untoward medical occurrence that, at any dose:

- Results in death,
- Is life-threatening,
- Requires in-patient hospitalization or prolongation of existing hospitalization,
- Results in persistent or significant disability/incapacity,
- Is a congenital anomaly/birth defect, or
- Is an important medical event

NOTE: The term "life-threatening" in the definition of "serious" refers to an event in which the patient was at risk of death at the time of the event. It does not refer to an event that hypothetically might have caused death if it were more severe.

Medical and scientific judgment should be exercised in deciding whether expedited reporting is appropriate in other situations, such as important medical events that may not be immediately life-threatening or result in death or hospitalization but may jeopardize the patient or may require intervention to prevent one of the other outcomes listed in the definition above. *These should also usually be considered serious.* Examples of such events are intensive treatment in an emergency room or at home for allergic bronchospasm, blood dyscrasias or convulsions that do not result in hospitalization, or development of drug dependency or drug abuse. The development of C-SSRS suicidal ideation type 4 (intent) or type 5 (specific plan and intent) any time after consenting to the study should always be reported as an SAE. Additionally, since only Types 1 and 2 are allowed at Screening or Baseline, the development of C-SSRS type 3 (method but no plan or intent) after consenting should always be reported as an AE.

Any death occurring during the study, during the per-protocol follow-up period, or reported to the Investigator after study participation (no required post-study time limit) must be reported to Tonix or its designee(s) immediately, whether or not it is considered treatment-related. Initial SAE reports must be followed by detailed descriptions. These should include copies of hospital case records and other documents when requested. Telephone and e-mail reports must be confirmed promptly either by facsimile or by email. For reporting SAEs, Tonix’s designated Medical Monitor should be called, and the relevant forms submitted to [REDACTED] PV within 24 hours of the site’s awareness of the SAE. The contact information for the Medical Monitor is as follows:

[REDACTED]	[REDACTED]
[REDACTED]	[REDACTED]
[REDACTED]	[REDACTED]

[REDACTED]

[REDACTED]

The Investigator, or the sponsor or designee in the case of a central IRB, also must notify the ethics committee (EC)/IRB of the occurrence of the SAE, in writing, as soon as is practicable and in accordance with local law. A copy of this notification must be provided to Tonix or its designee.

In the event of an SAE that meets the criteria for expedited reporting, an investigational new drug (IND) Safety Report will be prepared for submission to the FDA.

Clinical investigators also have the authority to unblind their own SAE patients if/when the unblinded treatment information could impact the patient’s clinical management. There is a module within the Interactive Response Technology system for investigators’ use if “emergency” unblinding is required; however, the Investigator is requested to confer with the

Medical Monitor before taking any action. The need for emergency unblinding is not expected for this study, in light of the nature of the study drug.

14.4. Pregnancy

The active pharmaceutical product in TNX-102 SL is cyclobenzaprine HCl, which is in Pregnancy Category B (See [Appendix 2](#) for AMRIX[®] Package Insert). All pregnancies occurring during the study (after exposure to study drug) or within 28 days after discontinuation of study drug must be followed until resolution (i.e., birth or voluntary or spontaneous termination of the pregnancy). Any patient found to be pregnant at any time during the study will be withdrawn from the study immediately. Any pregnancy outcome that meets the criteria for an SAE will be reported as an SAE.

15. PROCEDURES FOR MODIFYING THE PROTOCOL OR TERMINATING THE STUDY

15.1. Protocol Modifications and Deviations

The Investigator will make all reasonable efforts to comply with the written protocol and protocol amendments. All protocol modifications must be reviewed and approved by the appropriate EC/IRB before the revised protocol can be implemented. Emergency revisions that eliminate an apparent hazard to patients do not require preapproval by the EC/IRB. However, the EC/IRB must be notified, in writing, as soon as possible after the modification has been made. A copy of this communication must be forwarded to Tonix.

15.2. Study Termination

The study may be prematurely terminated at any time at the discretion of Tonix, its designee, or the Principal Investigator. Should premature termination be considered necessary, written notification documenting the reason for study termination will be provided, and specific procedures for termination will be arranged. Circumstances that may warrant premature study termination include, but are not limited to, the following.

- Determination of unexpected, significant, or unacceptable risk to patients
- Failure to enter patients at an acceptable rate
- Insufficient adherence to the requirements of the protocol
- Insufficient provision of complete and evaluable data
- Plans to modify, suspend, or discontinue development of the study drug

In the event that the study is terminated prematurely, all study materials must be returned to Tonix or its designee.

16. ETHICAL CONSIDERATIONS

16.1. Ethical Conduct of the Study

This protocol is written in accordance with the principles established by the 18th World Medical Assembly General Assembly (Helsinki, 1964) and amendments and clarifications adopted by subsequent General Assemblies. The Investigator will make sure that the study described in this protocol is conducted in full conformance with those principles, the protocol, current FDA regulations, ICH Good Clinical Practices (GCP) guidelines, Good Laboratory Practices (GLP) guidelines, local ethical and regulatory requirements, including the Federal Food, Drug and Cosmetic Act, US applicable Code of Federal Regulations (title 21), any EC requirements relative to clinical studies. As required by the US FDA, the study drug may not be shipped to any participating Investigator until the requisite study documentation has been submitted to the IND.

Should a conflict arise, the Investigator will follow whichever law or guideline affords the greater protection to the individual patient. The Investigator will also make sure he or she is thoroughly familiar with the appropriate administration and potential risks of administration of the study drug, as described in this protocol and the Investigator's Brochure, prior to the initiation of the study.

16.2. Ethics Committee/Institutional Review Board (EC/IRB) Review

The EC/IRB must be a properly constituted board or committee operating in accordance with 21 CFR Part 56, "Institutional Review Boards." This protocol, any protocol amendments, the associated informed consent forms, and the informed consent procedures must be submitted to the EC/IRB for review and approved before the enrollment of any patient into the trial.

All types of patient recruitment or advertising information must be submitted to Tonix or its designee and to the EC/IRB for review and approval prior to implementation. EC/IRB approval of any protocol amendments must be received before any of the changes outlined in the amendments are put into effect, except when the amendment has been enacted to eliminate a potential hazard to study patients. In such cases, the chair of the EC/IRB should be notified immediately and the amendment forwarded to the EC/IRB for review and approval.

16.3. Written Informed Consent

It is the responsibility of the Investigator to obtain signed written informed consent from each potential study patient prior to the conduct of any screening or other study procedures. This written informed consent will be obtained after the methods, objectives, and potential risks of the study have been fully explained to the potential patient. The Investigator must explain to each patient that he or she is completely free to refuse to enter the study or to withdraw from it at any time. NOTE: Patients on antidepressant therapy should be warned of a potential serious drug interaction and should be advised to contact their study site immediately if they experience any symptoms that might represent possible serotonin syndrome, including fever, confusion or agitation, hallucinations, sweating, high or low blood pressure, rapid heart rate, tremor, muscle rigidity or nausea, vomiting or diarrhea.

The patient should also be asked in the ICF for permission for the Principal Investigator or his designee to contact the patient's other personal physicians, as appropriate, concerning participation in the study.

The method of obtaining and documenting informed consent and the contents of the ICF will comply with ICH GCP guidelines, the requirements of 21 CFR Part 50, "Protection of Human Subjects," the Health Insurance Portability and Accountability Act (HIPAA) regulations, and all other applicable regulatory requirements. A properly executed written ICF shall be read, signed, and dated by each patient prior to entering the trial or prior to performing any study procedure. The original signed and dated ICF will be kept on file at the study site. Patients will be given a copy of the signed ICF and will be informed of any new developments during the course of the study that might influence their continued participation in the study.

The Investigator or a qualified designee will be available to answer each patient's questions throughout the study, and all questions must be answered to the patient's satisfaction. If the protocol is amended and a revised ICF is introduced during the study, each patient's further consent must be obtained. The new version of the ICF must be approved by the EC, prior to subsequently obtaining each patient's consent.

Receipt of written informed consent will be documented in each patient's or potential patient's CRF. The signed ICF must remain in each patient's study file and must be available for verification by study monitors at all times.

Separate written, signed informed consent must be obtained if the patient is to participate in the optional pharmacogenomic assessment.

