8. Based on screening laboratory results, thyroid-stimulating hormone (TSH) > 1.5 times the upper limit of normal or aspartate aminotransferase (AST) or alanine aminotransferase (ALT) > 2 times the upper limit of normal; or, in the Investigator's opinion, evidence of a clinically significant laboratory abnormality based on Screening laboratory tests or medical history.
9. Diagnosed with clinically significant and currently relevant cardiac disease (e.g., significant arrhythmia; heart block; heart failure; symptomatic coronary artery disease), recent myocardial infarction [within the past 2 years]) or QTcF > 450 msec (male) or > 470 msec (female) on the screening electrocardiogram (ECG).
10. The patient has a known current clinically significant systemic infection (e.g., HIV, hepatitis).
11. The patient is currently receiving or is expected to need systemic corticosteroids (>5 mg prednisone or equivalent per day) or has received acute treatment with systemic or locally injected corticosteroids within 28 days of the Baseline visit, or is likely to require such treatment during the study.
12. The patient has received tender point, trigger point or other local injections with anesthetic agents (or corticosteroids, as per EC#11) within 28 days of the Baseline visit, or is unable to refrain from such injections during the study.
13. The patient is unable to successfully wash-out of the following medications during screening, or wash-out is inadvisable: monoamine oxidase inhibitors (30 days), levomilnacipran, anticonvulsants (except when used for migraine prophylaxis), amphetamine mixed salts, weight loss agents such as phentermine and diethylpropion, muscle relaxants (e.g., methocarbamol, baclofen, carisoprodol), stimulants (e.g., methylphenidate, lisdexamfetamine, dextroamphetamine), mirtazapine, trazodone, nefazodone, St. John's wort, any medication known to be a strong CYP3A4 inhibitor ([Appendix 1](#)), or any of the medications listed in Inclusion Criterion #6.

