Due to the exclusion of all opioids during the Treatment Phase of the study, patients requiring opioids on a regular or frequent basis for any indication should not be considered. In addition, patients with neuropathic pain in addition to fibromyalgia should not be washed off of gabapentin, pregabalin or any other anticonvulsant, and therefore should not be considered for the study.

At Screening Visit 1 and after signing the written informed consent, any required washout should be discussed with the patient and plans made for an appropriate schedule for reducing/stopping any excluded medications. This down titration and withdrawal must be accomplished so that the patient is medication free for at least 21 days prior to randomization. This will provide 14 days off the excluded medication before the patient starts the 7-day run-in phase during which critical baseline efficacy data are collected by means of the daily diary. Any additional time required for down-titration would be in addition to this 21-day washout requirement. For this reason, patients can remain in screening for up to 35 days, which provides an additional 2 weeks for down-titration, if required. For extenuating circumstances, the duration of the Screening period may be increased to up to 49 days with Medical Monitor approval.

Other chronic prescription or over-the-counter medication not specifically excluded by an exclusion criterion may be continued in the study, provided that the patient has been on this medication for at least 30 days at a stable dose (except for allowed antidepressants, which require 90 days at stable dose) from the date of randomization, and usage is expected to remain stable throughout the study. Allowed medications include, but are not limited to, hormonal therapy (contraceptives and replacement therapy), anti-hypertensive agents, lipid-lowering medications, selective serotonin reuptake inhibitors (SSRI) and other allowed antidepressants (e.g., venlafaxine, desvenlafaxine, bupropion, vilazodone).

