Acetaminophen (up to 3000 mg/day) and non-steroidal anti-inflammatory drugs (NSAIDs) may be continued in a stable fashion for osteoarthritis or other allowed indications (e.g., aspirin for cardioprophylaxis), or used as needed for other sources of acute, minor pain. Note that acetaminophen and NSAIDs may be taken either on a regular basis, or on an as-needed (prn) basis; however, if used as-needed, the Investigator should ascertain the patient's typical pattern of usage (e.g., average dosage and frequency per defined time interval) so that this information can be recorded on the CRF. Any significant change in the patient's usage of any medication,

including those taken only as needed, should result in an update to the CRF. The CRF entry for any prn medication is expected to include an estimation of the patient's average dosage and frequency per defined time interval.

Patients on allowed antidepressants due to a history of depression should only be considered for the study if no changes in antidepressant agent or dose have occurred during the 90 days leading up to randomization, and no changes are anticipated or planned during the treatment phase of the study. In addition, FM patients with comorbid depression who are being treated with duloxetine, milnacipran, levomilnacipran, monoamine oxidase inhibitors, or tricyclic antidepressants should in general not be considered for the study since washout of these agents could destabilize their psychiatric status.

NOTE: Participating patients receiving treatment with antidepressants should be cautioned about the possibility of serotonin syndrome, which has been reported in patients receiving cyclobenzaprine with SSRIs, serotonin-norepinephrine reuptake inhibitors (SNRI) and related agents. This will be included in the ICF.

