5 WARNINGS AND PRECAUTIONS

5.1 Serotonin Syndrome

The development of a potentially life-threatening serotonin syndrome has been reported with cyclobenzaprine when used in combination with other drugs, such as selective serotonin reuptake inhibitors (SSRIs), serotonin norepinephrine reuptake inhibitors (SNRIs), tricyclic antidepressants (TCAs), tramadol, bupropion, meperidine, verapamil, or MAO inhibitors. The concomitant use of AMRIX with MAO inhibitors is contraindicated [see *Contraindications* (4)]. Serotonin syndrome symptoms may include mental status changes (e.g., confusion, agitation, hallucinations), autonomic instability (e.g., diaphoresis, tachycardia, labile blood pressure, hyperthermia), neuromuscular abnormalities (e.g., tremor, ataxia, hyperreflexia, clonus, muscle rigidity), and/or gastrointestinal symptoms (e.g., nausea, vomiting, diarrhea). Treatment with AMRIX and any concomitant serotonergic agents should be discontinued immediately if the above reactions occur and supportive symptomatic treatment should be initiated. If concomitant treatment with AMRIX and other serotonergic drugs is clinically warranted, careful observation is advised, particularly during treatment initiation or dose increases.

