17 PATIENT COUNSELING INFORMATION

See FDA-approved patient labeling (Patient Information).

- Instruct patients to swallow AMRIX capsules intact or to sprinkle capsule contents on a tablespoon of applesauce and swallow immediately without chewing.
- Advise patients to stop taking AMRIX and to notify their physician right away if they experience symptoms of an allergic reaction, such as difficulty breathing, hives, swelling of face or tongue, or itching.
- Advise patients that AMRIX should not be taken with MAO inhibitors or within 14 days after their discontinuation.
- Caution patients about the risk of serotonin syndrome with concomitant use of AMRIX and other drugs, such as SSRIs, SNRIs, TCAs, tramadol, bupropion, meperidine, verapamil, or MAO inhibitors. Advise patients of the signs and symptoms of serotonin syndrome [see Warnings and Precautions (5.1)] and instruct patients to seek medical care immediately if they experience these symptoms.
- Advise patients to stop taking AMRIX and to notify their physician right away if they experience arrhythmias or tachycardia.
- Advise patients that AMRIX may enhance the impairment effects of alcohol. These effects may also be seen if AMRIX is taken with other CNS depressants.
- Caution patients about operating an automobile or other hazardous machinery until it is reasonably certain that AMRIX therapy will not adversely affect their ability to engage in such activities.
- Advise patients to take AMRIX at approximately the same time each day.

Distributed By:
Teva Pharmaceuticals USA, Inc.
North Wales, PA 19454

Manufactured By:
Adare Pharmaceuticals, Inc.
Vandalia, OH 45377

AMR-010

Rev. 4/2019

US Patent Nos. 7387793, 7544372, 7790199, 7820203, 7829121, 8375410, 9399025

© 2004-2019 Teva Pharmaceuticals USA, Inc.

All rights reserved.

PATIENT INFORMATION

AMRIX® (am-rix)
(cyclobenzaprine hydrochloride extended-release capsules)

What is AMRIX?

AMRIX is a prescription medicine used along with rest and physical therapy to help treat muscle spasm due to acute, painful musculoskeletal problems.

AMRIX should only be used for up to 2 or 3 weeks. It is not known if AMRIX is effective when used for longer periods.

It is not known if AMRIX is safe and effective in children.

Do not take AMRIX if you:

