- are allergic to cyclobenzaprine or any of the ingredients in AMRIX. See the end of this Patient Information leaflet for a complete list of ingredients in AMRIX. Talk to your healthcare provider or get medical help right away if you have symptoms of an allergic reaction such as:
 - difficulty breathing
 - hives
 - swelling of your face or tongue
 - itching
- are taking certain antidepressants, known as monoamine oxidase (MAO) inhibitors or it has been 14 days or less since you stopped taking a MAO inhibitor. Ask your healthcare provider or pharmacist for a list of these medicines if you are not sure.
- have had a recent heart attack
- have heart rhythm problems (arrhythmias)

continued

AMRIX® (cyclobenzaprine hydrochloride extended-release capsules)

- have heart failure
- have an overactive thyroid (hyperthyroidism)

Talk to your healthcare provider before taking this medicine if you have any of the conditions listed above.

Before taking AMRIX, tell your healthcare provider about all of your medical conditions, including if you:

- have a history of eye problems including glaucoma
- have heart problems or have had a heart attack
- have liver problems
- have trouble emptying your bladder (urinary retention)
- are pregnant or plan to become pregnant. It is not known if AMRIX will harm your unborn baby.
- are breastfeeding or plan to breastfeed. It is not known if AMRIX passes into your breast milk. Talk to your healthcare provider about the best way to best way to feed your baby if you take AMRIX.

Tell your healthcare provider about all the medicines you take including prescription and over-the-counter medicines, vitamins, and herbal supplements. Especially tell your healthcare provider if you take:

- a medicine to treat depression, mood, anxiety, psychotic, or thought disorders
- a pain medicine called tramadol or meperidine
- barbiturates or other medicines that depress your central nervous system (CNS depressants)
- a medicine that prevents nerve impulses (anticholinergic medicines)
- a medicine to help quit smoking called bupropion
- a blood pressure medicine called verapamil

Know the medicines you take. Keep a list of your medicines and show it to your healthcare provider or pharmacist when you get a new medicine.

How should I take AMRIX?

- Take AMRIX exactly as your healthcare provider tells you to take it.
- Your healthcare provider will tell you how much AMRIX to take and when to take it.

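### The targeted serotonin-syndrome caution in Protocol 9.1 and 16.3 covers antidepressant users only, although the appended label also names verapamil, which the protocol permits

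*Protocol*

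**What the plan says.** Two notes in the protocol carry the targeted caution.

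- Section 9.1: "Participating patients receiving treatment with antidepressants should be cautioned about the possibility of serotonin syndrome". It mentions SSRIs, SNRIs and related agents, and adds: "This will be included in the ICF".
- Section 16.3: "Patients on antidepressant therapy should be warned of a potential serious drug interaction". This note also holds the symptom list and the advice to contact the site at once.

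The AMRIX label, the reference product's label reproduced in Appendix 2, goes wider. After SSRIs, SNRIs and tricyclics, its section 5.1 continues with "tramadol, bupropion, meperidine, verapamil, or MAO inhibitors". Section 7 repeats the list. Section 17 makes it a counselling instruction: "Caution patients about the risk of serotonin syndrome with concomitant use of AMRIX and other drugs", again naming verapamil. The patient leaflet that follows tells patients to mention "a blood pressure medicine called verapamil".

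On permitted drugs, section 9.1 states: "Allowed medications include, but are not limited to, hormonal therapy (contraceptives and replacement therapy), anti-hypertensive agents". The CYP3A4 part of exclusion criterion 13 in section 8.3 reaches only "any medication known to be a strong CYP3A4 inhibitor".

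**The concern.** The sponsor already has a general duty to explain risks, yet chose to add a specific prompt for patients on an interacting drug. The same label that supports the prompt for antidepressants also names a blood pressure medicine that patients may be taking on entry. Staff who follow the two notes will look for antidepressants and have no prompt to look for verapamil.

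What is at stake is patient safety, on a small scale. The useful part of the 16.3 note is that it tells the patient to call between visits. From Week 2 the visits are four weeks apart, and telephone visits omit vital signs, although fever, blood pressure change and rapid heart rate are among the listed symptoms. Section 9.1 also allows required new medicines after randomization, so verapamil could be started after the consent discussion.

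**Working it through.** The plan states no figure on this point, so the check sets the texts side by side.

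**Step 1. Is verapamil permitted?**
- Anti-hypertensives are allowed as a class in section 9.1, at a stable dose for at least 30 days before randomization.
- Exclusion criterion 13 removes strong CYP3A4 inhibitors. Appendix 1 says these are the far-left column of its table, and verapamil stands in the moderate column.
- No exclusion criterion or prohibited-drug list names verapamil.
- It is therefore permitted, by class and by absence from the exclusions, though not by name.

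**Step 2. How does each entry on the label's list stand in the protocol?**
- MAO inhibitors: 30-day washout required.
- Tricyclics: withdrawn.
- Tramadol: withdrawn.
- Meperidine: excluded with the opioids.
- SSRIs: permitted, and covered by the notes.
- SNRIs: duloxetine, milnacipran and levomilnacipran are washed out. Venlafaxine and desvenlafaxine are permitted and covered.
- Bupropion: permitted, and named in 9.1 as an antidepressant, so covered in that use. The leaflet also describes it as an aid to stop smoking, and for that use the notes are less clear.
- Verapamil: permitted, and outside both notes.

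Of the eight entries, four are removed by default, three are permitted and covered as antidepressants, and one is permitted and not covered: 4 + 3 + 1 = 8.

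**Step 3. Could the phrase on related agents in 9.1 take in verapamil?** It follows SSRIs and SNRIs in a sentence addressed to antidepressant users. A blood pressure medicine is not a natural reading of it.

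**Step 4. How many patients?** The documents do not say. As a conversion only, each 1% of the planned 470 is 0.01 × 470 = 4.7 patients, and half of that, 4.7 / 2 = 2.35, would be on active drug. No prevalence is assumed.

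**Step 5. Dose.** The trial's full dose against the label's doses is 5.6/30 = 0.19 and 5.6/15 = 0.37. These are nominal milligram ratios between a sublingual tablet and an oral capsule. They are not risk ratios.

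**The case against.** The case for leaving the text alone is fair, and much of it stands.

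- Section 16.3 requires potential risks to be fully explained to every patient, and the note adds emphasis without narrowing that duty. Section 16.1 requires the investigator to know the risks described in the protocol, which includes Appendix 2, and in the Investigator's Brochure.
- Section 9.1 places the caution in the consent form, which every patient reads and keeps. A verapamil user may well see it. Neither the form nor the Brochure could be reviewed.
- Exclusion criterion 9 removes patients with significant arrhythmia, heart block, heart failure or symptomatic coronary disease, and so some patients who might take verapamil.
- The label covers a different formulation at higher doses. Its drug list is illustrative and carries no event rate for the interaction.

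These points limit the size of the gap but do not close it. The text that 9.1 promises for the consent form is itself addressed to antidepressant users, and no protocol sentence tells staff to act on the label's counselling section.

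A reader might go further and infer that verapamil users are left unwarned. The documents do not show that, because the general duties and the unseen consent form may reach them. A reader might also infer the same gap for tramadol and meperidine. Opioids are excluded by default, acute need is handled with the Medical Monitor under 9.1, and SAP 4.4.1 has the patient contact the site immediately. That route is remote and needs no added text.

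**Conclusion.** The point holds as a small gap in safety wording and a cheap improvement. The two notes are narrower than the protocol's own appended safety source for one permitted drug. Bupropion taken to stop smoking deserves explicit mention so that the antidepressant wording is not read too narrowly.

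This rests on verapamil being permitted through its class and its moderate CYP3A4 listing, and on the notes meaning what they say about their target group. It does not rest on any estimate of exposure or harm, since the number of users is unknown. It gives no ground for excluding verapamil. Eligibility, endpoints, analyses and the SAP are unaffected.

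**What to change.** In Protocol 16.3 and 9.1, change the target group to: *patients taking an antidepressant (including bupropion for any indication) or verapamil, whether at consent or started during the study*. Keep the existing symptom list and the advice to contact the site. Then check the consent form, and align its sentence only if it is limited to antidepressant users.

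The cost is a short amendment, which section 15.1 requires the EC/IRB to review and approve. If the consent form has to change, section 16.3 also requires EC approval of the new version and each patient's further consent. That is the only substantial cost, and it arises only if the form proves equally narrow.
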